Cover page

Official Project Title: Reducing Pesticide Exposures in Child Care Centers

NCT # 03319927

Document: Study Protocol

Document Date: 8/13/2025

Study Protocol

UCSF IRB Study Application Section 8.0

8.2 HYPOTHESIS: Describe the hypothesis or what the study hopes to prove (Help Text updated 9/13):

1. Child care center staff who attend the IPM workshop will have significantly increased knowledge of IPM and hazards of pesticide use compared to their pre-workshop knowledge and compared to the control center staff.
- 2.: Post-intervention, the IPM intervention child care centers will have (a) higher numbers of written IPM policies, (b) more IPM practices, (c) fewer pest problems, and (d) higher director self-efficacy for pest management compared to pre-intervention and compared to the control centers.
3. Post-intervention, the IPM intervention child care centers will have lower concentrations and loadings of pesticides in dust compared to pre-intervention and compared to the control centers.
4. Post-intervention, children's personal exposure to pesticides, as measured by silicone wristbands, will be lower compared to pre-intervention and compared to that of children in the control centers.

8.3 AIMS: List the specific aims:

1. To determine if a nurse-led IPM workshop improves child care center staff's IPM knowledge.
2. To determine if an IPM intervention in child care centers (a) increases the number of IPM policies, (b) increases IPM practices, (c) decreases pest problems (i.e., number of pests present, pest debris), and (d) increases director's self-efficacy.

3. To determine if an IPM intervention reduces pesticide contamination in the intervention child care centers compared to the control centers.
4. To determine if an IPM intervention reduces children's and teachers' exposure to pesticides in the intervention child care centers compared to the children in the control centers.

8.4 DESIGN: Briefly describe the study design (e.g., observational, interventional, randomized, placebo-controlled, blinded, cross-over, cross-sectional, longitudinal, pharmacokinetic, etc.):

A randomized control study will be conducted and include 90 child care centers in four CA counties enrolled in five 9-month cycles over five years. The counties will be matched on rates of poverty, number of children under age five, and annual pesticide usage. The matched counties will be randomly assigned to an IPM intervention or an active control intervention (i.e. physical activity). During the 7-month Intervention phase, trained child care health consultants will host one workshop per center on the intervention topic (IPM or physical activity) and conduct seven monthly consultations per center starting with the center director and the child care health consultant setting center-specific goals.

The 'Follow-Up Study' will assess IPM practices, pests, and pesticides in all of the enrolled child care centers. The directors will complete surveys, the research staff will conduct observations, and a researcher will collect dust samples in the child care centers the same season and month as the baseline period.

BACKGROUND AND SIGNIFICANCE: Briefly provide the background and significance of this study (e.g. why is this study needed) (space limit: one page):

Children exposed to pesticides early in life are at risk for long-term cognitive, neurological, respiratory, and developmental problems.(Bouchard et al., 2011; Lanphear, Vorhees, & Bellinger, 2005; Liu & Schelar, 2012; Makri, Goveia, Balbus, & Parkin, 2004) Exposure to low-dose chronic indoor residential pesticides during early childhood is associated with an increased risk of leukemia and lymphoma.(Chen, Change, Tao, & Lu, 2015) Young children are vulnerable to pesticides because their organs are still developing, (Grandjean et al., 2015; Moya, Bearer, & Etzel, 2004) they spend time close to the ground where pesticides accumulate,(U.S. Environmental Protection Agency, 2007) and they have a higher intake of air, water, and food per unit of body weight compared with adults.(Bearer, 2000) The majority of children in the United States under six years of age, over 13 million, spend time in out-of-home settings,(Mamedova & Redford, 2015) with many preschool-age children spending 50% of their waking weekday hours in child care programs.(Laughlin, 2013) Several studies show that children are exposed to harmful pesticides in child care environments,([name] et al., 2012; Gilden, MeElroy, Friedmann, Witherspoon, & Paul, 2015; Kim et al., 2013; Tulve et al., 2006) where pesticide exposures are in some cases higher than in homes.(M. Morgan et al., 2007) Integrated pest management (IPM) is an approach to managing pests focused on preventing infestations. Pesticides are used as a last resort and primarily in self-contained bait stations, which do not contaminate indoor environments. IPM programs in homes have reduced pesticide exposure to young children by up to 50%. ([name] et al., 2012; Mir, Finkelstein, & Tulipano, 2010) (Williams et al., 2006)

Several child care-based IPM intervention studies have shown increases in staff's IPM knowledge, policies, and practices;(Anderson, Glynn, & Enache, 2010; Fournier & Johnson, 2003; Mir et al., 2010; [name] et al., 2012) however, these studies did not include control groups or assess changes in center- or child-level pesticide exposure. Pesticide exposure will be measured by dust samples in child care centers and child-level exposures will be measured using silicone wristbands. Though pesticide biomarkers in urine or blood are considered the gold standard for exposure assessment, their use has limitations, and – importantly – many pesticides lack exposure biomarkers. Several of these biomarkers, like urinary metabolites of organophosphates, represent exposure to an entire class of pesticide but give no information about pesticide-specific exposure. Thus, wristband measures or individual pesticide exposures address the limitations of biomarkers to quantify pesticide exposures to individuals.

8.6 PRELIMINARY STUDIES: Briefly summarize any preliminary studies relevant to your proposed research (space limit: one half page):

[name] conducted a survey of 637 randomly-selected CA child care centers to assess pesticide use and pest management and found that 75% of respondents were not familiar with IPM and 55% of the respondents reported using pesticides to control pests; 47% used sprays or total-release foggers. ([name] et al., 2010). The results of this survey informed our work in developing an IPM Toolkit for child care center staff in CA as well as a State-approved IPM course for licensed pest management professionals.

Drs. [name] and [name] led a multidisciplinary team of inter-disciplinary experts to design an evidence-based, user friendly IPM Toolkit for Early Care and Education Programs for child care providers and health services/facilities managers.([name] et al., 2012) The Toolkit includes an IPM curriculum, pest-specific information sheets, posters, and IPM Checklist. The pest-specific information sheets include the top pest problems identified in [name] survey described above. The Toolkit is available in English and Spanish (cchp.ucsf.edu).

Drs. [name] and [name] conducted a pre- and post-evaluation study of a seven-month nurse-led IPM intervention using the IPM Toolkit for educational workshops for staff. Results shows a significant increase in staff knowledge on IPM practices (from 61% to 88%), reduced pest problems (a 42% decrease in live pests), and increased IPM practices (a 9% increase). However, the impact on pesticide exposure levels was not assessed.

In a study funded by the California Air Resources Board (CARB), [name] and colleagues measured several classes of pollutants in indoor air and dust in 40 CA child care facilities.([name] et al., 2012) Pesticides, including bifenthrin, chlorpyrifos, cis-permethrin, cypermethrin, dacthal, diazinon, piperonyl butoxide, sumithrin, and trans-permethrin, were detected in dust and/or air in 100% of the child care facilities.

[name] consulted on the first study to employ silicone wristband samplers specifically for assessment of pesticide exposures. One hundred adolescent girls wore wristbands (PSD) indoors and outdoors for one full week. PSDs from this study are currently being analyzed by [name] and her team at Oregon State University (OSU).

Our UCSF study team conducted a randomized control trial of the Nutrition And Physical Activity Self-Assessment for Child Care (NAP SACC) intervention in which nurse CCHCs provided educational workshops and monthly consultation on nutrition and physical activity content.(Benjamin et al., 2007) For the proposed study's attention control group, we will modify the NAP SACC intervention to mimic the time and intensity of the IPM intervention with a workshop, monthly consultation, and NAP SACC's anthropometric and physical activity measures.

The preliminary analysis of the dust samples collected in the child care centers in year 1, showed that there were no significant decreases in pesticides detected post-intervention compared to pre-intervention in the IPM vs. physical activity centers. It is not known if there were seasonal differences in pesticides detected pre- versus post-intervention. There were no post-intervention dust samples collected in the same season and month as the pre-intervention dust samples. Therefore, the

follow-up study will include an assessment of IPM practices, pests, and dust samples to assess long-term changes in pesticide exposure.

8.9 * PROCEDURES / METHODS: (REQUIRED)

Overview. The study participants include 90 child care center directors, 270 child care center staff, and 450 parents (mothers, fathers or legal guardians) and their preschool-age children, 3-5 years of age. The participants will be involved in the following procedures: (a) child care center directors will be interviewed by the UCSF research staff, (b) child care center staff will attend an educational workshop and complete a knowledge survey before and after the workshop, (c) parents/guardians will be given surveys to complete on their own or by interview about their family and child demographics and pesticide use at home, (d) children will have their height, weight, and waist circumference measured twice along with measurement of individual exposures using silicone wristbands before and after the intervention, and (e) research staff will collect dust samples in each center and conduct observations of the child care center environment and children's physical activity before and after the intervention.

Staff Roles. The research assistants' (RA) and child care health consultants' (CCHC) activities include:

1. Attend a one-day training on the intervention and data collection protocols. (CCHC/RA). The RA will achieve 90% inter-rater reliability with the PI on 2 observation instruments (Health and Safety Checklist and IPM Checklist).
2. Recruit child care directors through the local Resource and Referral Agencies (CCHC/RA).
3. Obtain signed consent forms from the child care directors (CCHC).
4. Identify 5 children per center and contact families and obtain signed consent forms. (CCHC/RA)
5. Conduct child care director interviews pre- and post-intervention (CCHC).
6. Complete Health and Safety and IPM Checklists. (RA)
7. Write-up the summary of the Checklist with photographs and narrative. (RA)
8. Collect anthropometric measures of the children, including height, weight, and waist circumference on 5 children per center pre- and post-intervention. (CCHC/RA)
9. Collect dust samples in the center and wristband measures for 5 children per center over two days pre- and post-intervention. (RA and CCHC together)

10. Prepare and provide 2 workshops for child care staff. (CCHC)
11. Review Checklist summaries with the director and establish 3-5 goals of the intervention. (CCHC)
12. Assist the child care directors to develop written health and safety policies. (CCHC)
13. Conduct monthly on-site (x3) or off-site (x3) (email, mail, phone) consultation. (CCHC)
14. Complete post-intervention measures (interview, dust and silicone wristbands, activity observations, anthropometric measures). (CCHC/RA)
15. Complete post-intervention observational Checklists (IPM Checklist, Health and Safety Checklist) and write up summary report comparing pre- and post-intervention findings. (RA)

Baseline Assessment. During the Baseline Assessment stage at each center, an experienced research assistant (not a CCHC) will complete *inspection checklists* in each center. The IPM Checklist,([name] et al., 2012) Health and Safety Checklist for Early Care and Education Programs,([name], 2015) and Policies Checklist, utilized in prior studies, will be completed in all centers. The *IPM Checklist* includes 73 items with 8 subscales (outdoor: garbage, exterior, play area; indoor: kitchen, bathrooms, play areas, storage, staff area) and for each subscale the pest problems are observed in that location by type and number or pest debris. Cronbach's alpha coefficients for the subscales showed a range of moderate reliability ($r=.38$ to $.61$)([name] et al., 2016a). For this project, the IPM Checklist will include additional items to identify the pesticides stored and used on-site by child care or facility staff, including active ingredients and U.S. EPA pesticide registration numbers. The *Health and Safety Checklist* includes 66 items in three relevant subscales on sanitation (e.g., handwashing, air quality), supervision (e.g., child-staff ratios), and equipment and furnishings (e.g., physical activity indoors and outdoors). The Health and Safety *Policy Checklist* assesses written policies for each child care center based on the national health and safety standards.([name] et al., 2009) The relevant policies for this study include IPM and physical activity.

During this period, the nurse CCHC assigned to the child care center will *interview the child care center's director* to collect information on personal (e.g., education level, years of experience) and center (e.g., staff turnover, facility age) demographics; the center's pest problems, pesticide use practices, and IPM policies and practices; the center's physical activity programs for children; the center's food service responsibilities, menus, and feeding practices; and the center's cleaning products, cleaning routines, and maintenance practices. The CCHC will also ask the director to complete a *self-efficacy survey* based on Bandura's SCT.(Bandura, 1977)

The CCHC will also conduct two forms of *environmental sampling* and collect *anthropometric measurements on children* during the Baseline Assessment stage. The CCHC will conduct *dust sampling* using an HVS3 vacuum sampler to collect dust from a carpeted area in the central child care room.(JW Roberts et al., 1991) In years 1 and 2 and for 2 centers in

year 3, parents/guardians of enrolled children will be issued two ***silicone wristbands*** each: a blue one which they will be asked to wear continuously for 5 days, both at home and at the center, including while bathing and sleeping, and a yellow one they will be asked to wear at the center only, for 5 days. During the 5 days, the children will wear both wristbands simultaneously, and the CCHC will be present to assist with sample collection. On day one, the nurse CCHC will measure participating children's height, weight, and waist circumference. On 2 days, CCHCs will assess children's activity level using the Observation System for Recording Activity in Preschools (OSRAP). Using the OSRAP, CCHC observers will record the intensity of children's physical activity (1=stationery to 5=fast), location of activity, context of activity (teacher directed, child initiated), and interactions (none, child peer, provider, other adult). For all of the enrolled children, the CCHC will also assure that children's yellow wristbands are removed and sealed in child-specific storage bags at the end of each sampling day, and that the correct wristband is placed on the correct child on the 5 in-center collection days. All of the enrolled children will wear a wristband in the child care center over 5 days for at least 30 total hours. At some point during their child's sampling period, at a time convenient for them, parents/ guardians will be asked to complete a questionnaire in English or Spanish regarding their child's demographic and health characteristics, diet and physical activity habits at home (e.g., organic vs. conventional diet, indoor vs. outdoor play), home pesticide use, and any other possible sources of pesticide exposure, including through parents'/ guardian's occupations, residence with farmworkers, or residence near agricultural fields. Parents/guardians will also be asked to provide their home address for geocoding. Questionnaire items will be modeled upon pesticide exposure questions asked in other CERCH studies, including Center for Health Assessment of Mothers and Children of Salinas (CHAMACOS) and the recent silicone wristband study noted in Preliminary Studies. Two child care teachers per center will wear silicone wristbands for five days or 30 hours to measure pesticide levels.

Post-Intervention Phase. During this phase, a research assistant will re-assess the center using the same observational checklists described for the Baseline Assessment, and the CCHC will also repeat all other aspects of Baseline Assessment data collection, including a director interview, the self-efficacy survey, dust collection, silicone wristband collection (children and teachers) and its attendant data collection from families, and anthropometric measurements. At Post-Intervention, however, no new children will be enrolled to participate. The same families who participated at Baseline will be invited to participate again, provided their child still attends the center and intends to be present on the sampling days.

Follow-up Study. We will also conduct a one-year follow-up study on pesticide exposure for all of the intervention centers, including both dust analyses and assessment of pests and pesticide products .

Sampling Procedures. The silicone wristbands will be sent de-identified to [name] laboratory at Oregon State University and the child care center's dust samples will be sent to Southwest Research Institute (SwRI) located in San Antonio, TX for analysis of multiple pesticides. They will be analyzed within a year of data collection and we will store the amount of

wristband or dust that is left over for 5 years to use in possible future analyses of other environmental chemicals or health markers.

8.11 INSTRUMENTS: List all questionnaires, surveys, interview, or focus group guides that will be used for this study:

If the instruments are not complete or not available because they will be developed as part of this study, describe the basic content or include an outline and submit the final versions to the IRB with a modification for approval prior to use.

1. IPM and Physical Activity (PA) Knowledge Survey – pre and post-workshop
2. IPM and PA Policy Checklist
3. Director interview
4. IPM Checklist ([name] et al., 2012)
5. Director IPM Interview
6. Director and child care provider Self-Efficacy ([name] et al., 2003) – modified Bandura
7. Demographic Survey for child care providers - sex, age, ethnicity,
8. Demographic Survey for parents - sex, age, ethnicity, BMI, health
9. CHAMACOS parent interview -modified as self-completed survey with major life events, physical activity
10. Child Anthropometrics
11. Dust samples ([name] et al., 2012)
12. Child activity measure modified OSRAP (A [name] et al., 2014)
13. Health and Safety Checklist for Early Care and Education Programs ([name] et al., 2015)
14. Pesticide Use Data - collected by the CA Department of Pesticide Regulation

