Specific Aim 3: To determine if an IPM intervention reduces pesticide contamination in the intervention IPM child care centers compared to the PA control centers. (a) **Unit of Analysis:** Child care centers. (b) **Dependent Variable:** Pesticide concentrations in dust. (c) **Independent Variables: Group, Time, and Cohort.** Tobit regression models were conducted with an additional random intercept term for child care center to account for correlations within centers across timepoints (baseline, post-intervention). The concentrations and detection of the 15 pesticides measured in dust were analyzed separately using the STATA command 'tobit'.

Specific Aim 4: To determine if an IPM intervention reduces children's exposure to pesticides in the IPM intervention child care centers compared to the children in the PA control centers. (a) **Unit of Analysis:** Enrolled children with complete wristband data at baseline and post-intervention aggregated by child care center. (b) **Dependent Variable:** Pesticides measured in children's wristbands worn at the child care. (c) **Independent Variables: Group, Time, and Cohort.** Pesticide concentrations analyzed in the silicone wristbands. (c) **Independent Variables: Group, Time, and Cohort.** Tobit regression models were conducted with an

additional random intercept term for child care center to account for correlations within centers across timepoints (baseline, post-intervention). The concentrations and detection of the 13 pesticides measured in dust were analyzed separately.

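### Hypothesis 4: a within-arm change in wristband pesticides can be measured but not attributed to the intervention rather than to season, so Aim 4 should be judged on the between-arm difference in change

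*Protocol*

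**What the plan says.** Protocol 8.2, Hypothesis 4, makes two comparisons joined by a conjunction: exposure by wristband "will be lower compared to pre-intervention and compared to that of children in the control centers". Protocol 8.3, Aim 4, and SAP Specific Aim 4 are both framed only against the control centers.

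The timing comes from Protocol 8.4. Centers are "enrolled in five 9-month cycles over five years", and the workshop and consultations take place "During the 7-month Intervention phase". Under Post-Intervention Phase, Protocol 8.9 has wristband collection repeated once after baseline. The SAP analyses "Enrolled children with complete wristband data at baseline and post-intervention aggregated by child care center", so there are two wristband time points. The independent variables listed for Aim 4 are Group, Time and Cohort. No interaction and no season or month term is named.

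Protocol 8.6 discusses season for the year-1 dust results: "It is not known if there were seasonal differences in pesticides detected pre- versus post-intervention". It adds that no post-intervention dust sample matched its baseline sample on season and month, and gives this as the reason for a follow-up study. Protocol 8.4 lists director surveys, observations and dust for that follow-up. Protocol 8.9 describes it as "including both dust analyses and assessment of pests and pesticide products". Neither description mentions wristbands.

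**The concern.** The protocol recognises that its schedule leaves season as a possible explanation for pre-post change in dust, and adds a visit to deal with it. Wristbands follow the same schedule and get no such visit. The pre-intervention limb of Hypothesis 4 is therefore open to season in either direction.

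- If the two limbs are read as separate claims, a purely seasonal fall would count as support for the first.
- If both limbs must hold, a seasonal rise could defeat the hypothesis even when the intervention works.

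The contrast that removes a shared seasonal shift is the difference between arms in change from baseline. The SAP does not name it for Aim 4, so a reader cannot tell which coefficient decides the aim.

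**Working it through.** The plan gives no seasonal effect size, power calculation or sample-size figure for this comparison, so there is no stated figure to reproduce.

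**1. Calendar.** The inputs are the 7-month intervention and the 9-month cycle (Protocol 8.4), which put the gap at 7 to about 9 months. With three-month seasons, all 12 start months were enumerated.

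| Gap (months) | Start months with both visits in the same season | Distance from the baseline calendar month |
|---|---|---|
| 7 | 0 of 12 | 12 − 7 = 5 months |
| 8 | 0 of 12 | 12 − 8 = 4 months |
| 9 | 0 of 12 | 12 − 9 = 3 months |
| 12 | 12 of 12 | 0 months |

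**2. What each contrast estimates.** Let δ be the intervention effect and s the seasonal shift between the two visits, on the log scale.

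- Change in the IPM arm = δ + s.
- Change in the control arm = s.
- Difference in change = δ, if s is the same in both arms; otherwise δ + (s in IPM − s in control).

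With δ = 0 and s < 0, the pre-intervention limb appears to be met. With δ < 0 and s > |δ|, it fails although the intervention works.

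**3. Can a month term separate δ from s?** Estimability was checked in a linear model with center effects, Time, Group-by-Time and one annual sine/cosine pair, at an assumed gap of 8 months.

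- All centers start in the same calendar month: the Time effect is not estimable, because the seasonal terms are collinear with Time. Group-by-Time is estimable.
- Start months staggered: both are estimable, but only because the model contains the month term.

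The documents do not give start months. Five 9-month cycles in five years would fit one start month each year, but that is an assumption.

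**4. Effect on a within-arm test (assumed inputs).** The SAP gives 85 centers for survey and observational data. An even split is 85/2 = 42.5, taken as 43. The number of centers with paired wristbands is not stated. Let k be the seasonal shift in SDs of center-level change, with no intervention effect and a two-sided 0.05 level. By normal approximation to a paired test:

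P(significant) = Φ(k√43 − 1.96) + Φ(−k√43 − 1.96)

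| k | P(significant) |
|---|---|
| 0 | 5% |
| 0.1 | 10% |
| 0.2 | 26% |
| 0.3 | 50% |
| 0.5 | 91% |

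With 42 to 45 centers, the k = 0.3 row runs from 49% to 52%. This is a simplification of the planned tobit model.

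**5. Largest apparent fall (assumed inputs).** For an annual sinusoid on the log scale with peak-to-trough ratio R, two samples d months apart differ by at most sin(πd/12) × ln R. The factor is 0.966 at 7 months, 0.866 at 8 and 0.707 at 9. The largest apparent fall is 1 − R^(−factor).

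| R | 7 months | 8 months | 9 months |
|---|---|---|---|
| 1.25 | 19% | 18% | 15% |
| 1.5 | 32% | 30% | 25% |
| 2.0 | 49% | 45% | 39% |

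These are upper limits at the least favourable start month. Averaged over start months, the absolute log difference is 2/π, about 64%, of the maximum. It is zero at some start months and is a rise as often as a fall.

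**The case against.** The strongest reply is that the design already contains the remedy. There is a concurrent control arm, sampled at the same two phases, and Aim 4 is framed against it in both documents. A seasonal fall shared by both arms would fail the second limb of Hypothesis 4, and neither document sets a pre-post-only success criterion for wristbands. This largely stands, and it limits the point to interpretation and specification. It does not remove the point: the pre-intervention limb remains something the protocol hopes to show, and the SAP does not say that Group-by-Time decides the aim.

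A reader might infer four stronger things that the documents do not support.

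- **That the pre-intervention limb cannot be answered at all.** Two measurements do show whether exposure was lower than before; what they leave open is the cause.
- **That Protocol 8.6 establishes a seasonal effect.** It says only that season is unknown, and only for year-1 dust. Its extension to wristbands is inferred from the schedule.
- **That season could mimic the reduction of up to 50% reported for IPM in homes (Protocol background section).** The 49% above follows from choosing a ratio of 2.0 at the worst start month and is not evidence.
- **That the between-arm contrast is itself distorted by unequal sampling months.** Nothing in the documents says the arms were sampled in different months. Equal seasonal patterns in the two arms remain an assumption, and with only four randomized counties it has thin support.

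**Conclusion.** The point holds as an issue of attribution and specification. Baseline and post-intervention wristbands are 7 to about 9 months apart, no wristband visit matched to the baseline season is described, and the listed Aim 4 model has no term that separates season from Time. A within-arm change therefore combines any intervention effect with any seasonal effect, of unknown size and direction. If a seasonal shift of 0.2 to 0.5 SD of change existed, a within-arm test would be significant 26% to 91% of the time with no intervention effect. Those figures rest on assumed shifts and an assumed 43 centers per arm. The between-arm difference in change remains interpretable provided both arms share the same seasonal pattern.

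**What to change.** State in the SAP that Aim 4 and Hypothesis 4 are judged on the between-arm difference in change from baseline, the Group-by-Time term. Report within-arm wristband change descriptively, with a sentence saying that it is confounded with season.

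The SAP is largely written in the past tense, so Hypothesis 4 should stay on record as it stands. The change should be documented, with its date and reason, rather than made by deleting half of the hypothesis.

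Add a sampling-month term only as a sensitivity analysis, and only if collection dates were recorded and sampling months vary across cycles or counties. The documents state neither. If all cycles share the same months, the term is collinear with Time and should be left out.

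The cost is wording, one named contrast and one less favourable pre-post claim. No visits or wristbands are added.
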